5.3.2 DURATION OF ANTIBIOTICS

Children randomised to oral step-down medication will simultaneously be randomised to receive a total antibiotic duration (IV plus oral from start of IV treatment, excluding any (oral/intramuscular) antibiotics taken in the community) of 4 vs 5 vs 6 vs 7 vs 8 days, except for those children in the Phase II PK trial (PediCAP-B) on co-amoxiclav 4:1 or 14:1 who will receive a total of 6 days of antibiotics. Exact numbers of tablets will be prescribed to complete this total duration based on the doses of IVs received, and the child's weight, plus one additional dose in case of lost tablets/vomited dose post-discharge.

See [Section 5.3.4.B](#) below for management of inadequate response or relapse on oral treatment. Parents/carers of children who are discharged clinically stable with remaining oral medication to complete their randomised course of antibiotics will be instructed to contact the study team if they have any concerns, lose more than one dose, or if the child has persisting symptoms.

5.3.3 DISPENSING AND ACCOUNTABILITY

The investigational medicinal product (IMP) will be stored separately from routine clinic drug supplies in a designated section of the pharmacy or other appropriate location, such as the emergency department, clinical research facility or ward at the study sites. The IMP will be designated for strict use for trial participants only, and stock will be audited intermittently during the trial at each site.

For all trial drugs, the designated trial pharmacist or nurse will confirm receipt of supplies prior to the commencement of the trial. Inventories will be conducted regularly, and logs returned to the CTU as detailed in the Pharmacy MOP.

Parents/carers will be provided with a full supply of drugs on discharge from hospital, sufficient to complete the randomised total duration of antibiotics exactly plus one additional dose.

Parents/carers will be requested to return any unused drug to the clinic at their 4 week visit.

Medication will be provided as tablets to be dissolved in water or other liquid (e.g. breastmilk). The pharmacist, clinician or research nurse will ensure parents/carers understand how the drugs must be given prior to discharge, and parents/carers will be given an information sheet before the child is discharged. This will include clear instructions that tablets must be taken as dispersed tablets and not swallowed whole, divided or crushed.

On no account should any drug assigned to a child be used by anyone else. Unused trial drug must be returned to the site if a child withdraws from treatment before completing their randomised duration of therapy.

All drugs dispensed and returned to the site should be documented on a treatment log. At each site, a named person (pharmacist or research nurse) will be required to maintain complete records of all study medication dispensed and returned. The designated pharmacist/nurse will, on receipt of supplies prior to the start of the trial, conduct an inventory and complete a receipt.

Procedures for drug distribution, labelling, accountability and destruction will be detailed in the PediCAP Pharmacy MOP. Drug accountability will be regularly monitored and the remaining stocks checked against the amounts dispensed. At the end of the study, all remaining investigational drugs will be destroyed. CTU will monitor drug accountability centrally and during site visits.

5.3.4 DOSE MODIFICATIONS, INTERRUPTIONS & DISCONTINUATIONS

Amoxicillin and co-amoxiclav are both active drugs that are routinely given to children with CAP. The doses given to the children in all the study groups are broadly aligned with the internationally recommended amoxicillin dosing range (see [Section 0](#)).

5.3.4.A Stopping Drug Early

Adverse events caused by drug toxicity leading to a treatment change are expected to be rare, and should be managed following local practice. In the situation when a penicillin allergic reaction is suspected (e.g. typical, indicative skin rash) it would be customary to switch to an antibiotic of a

different class. Children should remain in the study for follow-up and should continue to follow the assessment schedule.

If they happen, severe allergic reactions (immediate type 1 reactions) are expected to occur early while the child is in hospital on a parenteral penicillin-based antibiotic regimen. Severe allergic reactions to either amoxicillin alone or in combination with clavulanate are very rare, but again are expected to occur while the child is in hospital. All parents/carers will be provided with telephone numbers for the study team and be told to return with the child to hospital if there are any acute events. Delayed drug reactions are generally mild and self-limiting and resolve with discontinuation of the drug. The onset of mild delayed reactions is most common at 10-14 days after treatment exposure, i.e. after trial treatment has already been completed. Delayed drug reactions may occur earlier as a reaction to re-exposure (i.e. in children re-exposed to amoxicillin). In severe cases, immediate discontinuation and future avoidance of the suspected trigger is recommended.

In cases where there is an issue with tolerability of the trial medication resulting in recurrent spitting or gagging, the child should be switched to an alternative amoxicillin or co-amoxiclav formulation where available locally, or to another antibiotic if not available locally and the child is still assessed to be in need of continued treatment. This mirrors routine clinical practice, and the decision to continue antibiotic treatment is based on the assessment of the child. Requirement to switch from the IMP to an alternative formulation of amoxicillin or co-amoxiclav for these reasons will be reported on CRFs\worksheets for the reason of tolerability. All such children will continue follow-up in the trial, "off-study-drug, on-study" (see [Section 5.7](#) below).

5.3.4.B Inadequate Response or Relapse on Oral Treatment or Post-discharge

The management of potential inadequate response to the randomised antibiotic regimen and/or relapse after the completion of therapy as prescribed will be based on a range of potential scenarios. These will be fully described in the MOP, but example scenarios are included in [Section 0](#) below.

5.3.5 COMPLIANCE & ADHERENCE

Amoxicillin and co-amoxiclav are widely used worldwide for treatment of bacterial respiratory tract infections, with extremely low rates of toxicity. Mild unwanted side-effects, including diarrhoea and thrush, have been reported [48, 49], and these will be directly solicited. The importance of adherence should be reinforced at the time of dispensation of trial medication and during any subsequent contacts with the study team. Adherence and tolerability will be assessed during the week 1 (and week 2 if appropriate) telephone follow-up.

Amoxicillin suspension is the most commonly used single antibiotic formulation for the treatment of children globally [50]. In this study, older (and heavier) children will receive a relatively large number of tablets per single dose, but dispersed this should still be less volume than oral solution. The twice daily dosing schedule used is known to make administration of antibiotics to schedule easier for parents and improve compliance [51].

Adherence to the prescribed course, and tolerability of the dispersible tablets, will be assessed by adherence questions in telephone clinical assessments post discharge from hospital. The importance of adherence should be reinforced prior to discharge from hospital, and during telephone calls.

5.4 INADEQUATE RESPONSE TO TREATMENT

The management of potential inadequate response to intravenous antibiotics or the randomised antibiotic regimen and/or relapse after the completion of therapy as prescribed will be based on a

range of potential scenarios. These will be fully described in the MOP, but example scenarios are included in **Table 8** below.

Table 8: Example scenarios of inadequate response or relapse

TIMING	SCENARIO	ACTION*
DURING PRIMARY HOSPITAL ADMISSION OR WITHIN ORIGINALLY RANDOMISED TREATMENT COURSE		
Any time	Child clinically deteriorates, e.g. with severe respiratory distress or septic shock	Chest X-ray is strongly recommended. Treat with injectable antibiotics as per normal standards of care (e.g. moving to second line treatment regimen according to local standard of care).
	Positive blood culture or other test result suggesting more serious manifestation of severe CAP	Manage according to local standard of care (e.g. moving to different intravenous antibiotics, treating for longer than original randomisation depending on clinical status of the child).
After two days IV	No improvement in clinical status on IV therapy	Manage according to local standard of care (e.g. moving to cloxacillin if staphylococcal pneumonia is suspected, or to second-line, or repeating laboratory tests where available). Consider TB.
After oral switch	Child has persistent symptoms and signs of a respiratory tract infection after oral switch, e.g. with continued fever, tachypnoea, tachycardia, but remains clinically stable. Appears to be tolerating oral medication.	Continue oral medication as randomised: most likely infection is viral. Also consider evaluation for TB.
	Child has persistent symptoms and signs of a respiratory tract infection and is NOT tolerating oral medication due to severe persistent vomiting or diarrhoea	Switch to IV or injectable antibiotics as per normal standards of care.
AFTER DISCHARGE FROM PRIMARY ADMISSION OR AFTER COMPLETION OF INITIAL RANDOMISED COURSE		
Any time	Child has persistent symptoms of a mild respiratory tract infection, with no signs of pneumonia	No treatment for CAP. A child with persistent cough and fever for more than 2 weeks and signs of pneumonia after adequate antibiotic treatment should be evaluated for TB.
	Child has signs of pneumonia, and fulfils the diagnostic criteria of non-severe CAP	Treat as per normal standards of care. Consider TB.
	Child has signs of pneumonia, and fulfils the diagnostic criteria of severe CAP	Admit. Chest X-ray is strongly recommended. Treat with IV or injectable antibiotics as per normal standards of care. Consider TB.

* Regardless of action taken, children will continue to be followed up “on study-off study medication” until 28 days post-randomisation. See **Section 0**.

5.5 HANDLING CASES OF TRIAL MEDICATION OVERDOSE

Parents/carers of the children participating in the study should be counselled about the importance of taking the oral medications as prescribed. Although renal injury has been described in children after accidental amoxicillin overdose, this is rare even in single doses above 250mg/kg [44], which is much higher than the highest daily dose in PediCAP of 167 mg/kg/day. Parents/carers should contact the PediCAP team immediately if their child has been overdosed, to receive appropriate advice. Children will then be managed on a case by case basis, and toxicity will be managed in all randomised groups according to standard clinical practice. Instances of overdose with IMP will be deemed as a deviation from study procedure and a notable event (**Section 0**) and will be reported as such.

5.6 UNBLINDING / UNMASKING

PediCAP is an open label trial so unblinding/unmasking will not be necessary.

5.7 PROTOCOL TREATMENT DISCONTINUATION

In consenting to the trial, parents/carers are consenting to trial treatment, trial follow-up and data collection for their child. However, an individual child may stop randomised trial treatment early, or be stopped early for any of the following reasons:

- Inadequate response or relapse on trial treatment
- Unacceptable toxicity or adverse event
- Intercurrent illness that prevents further treatment
- Any change in the child's condition that justifies the discontinuation of trial treatment in the clinician's opinion
- Use of a medication that is essential for the child's management with a known major or moderate drug interaction with the trial antibiotics
- Inadequate compliance with the protocol treatment in the judgement of the treating physician, including for reasons of tolerability, see **Section 5.3.4.A** above
- Overdose with trial drug
- Withdrawal of consent for treatment by the child or parent/carer

As the child's participation in the trial is entirely voluntary, they or their parents/carers may choose to discontinue the trial treatment **at any time without penalty or loss of benefits to which they are otherwise entitled**. The parent/carer/child **is not required to give a reason for discontinuing their child's trial treatment**; however, if possible, a reasonable effort should be made to establish this reason while fully respecting the child and family's rights.

Children stopping randomised trial treatment should remain in the trial for the purpose of follow-up and data analysis "on-study, off-study-treatment" (unless the parent/carer explicitly withdraws their consent from all stages of the trial) to contribute to the "intention-to-treat" analysis. Any other non-trial medication a trial child receives will be recorded on CRFs\worksheets. If a child is withdrawn from all follow-up, refer to **Section 6.6**.

Data will be kept and included for children who stop follow-up early.

5.8 TREATMENT DATA COLLECTION

Information about all antibiotics and concomitant medication received, including formulation, frequency, dose and reasons for change will be collected on the CRF\worksheet.

5.9 NON-TRIAL TREATMENT

All oral, intravenous, intramuscular and topical treatments for any condition are considered a concomitant medication, including blood transfusion.

5.9.1 MEDICATIONS PERMITTED

All necessary concomitant medications are allowed. Regular medications will be recorded at baseline. Parents will be asked to report the use of additional medications during follow-up telephone calls, including traditional medicines. If a medication with a known major or moderate drug interaction with amoxicillin (see [Section 5.9.2](#)) is essential for a child's management and cannot be replaced by a drug that does not have an interaction with amoxicillin, then the trial medication should be stopped and the concomitant medication used (see [Section 6.8](#)).

5.9.2 MEDICATIONS NOT PERMITTED

Medications with known interactions with amoxicillin, which include allopurinol, methotrexate and mycophenolate, are not used in otherwise healthy children in the target age group. In addition, amoxicillin may diminish the therapeutic effects of BCG and oral typhoid vaccines. These immunisations, if included in the immunisation schedules of participating sites, should be postponed until after completion of trial medication.

5.9.3 TREATMENT AFTER TRIAL EVENT

Treatment will be at the discretion of the responsible physician.

5.10 CO-ENROLMENT GUIDELINES

Co-enrolment in previous or future trials is considered in [Section 4.3](#).

6 ASSESSMENTS & FOLLOW-UP

6.1 TRIAL ASSESSMENT SCHEDULE

The frequency of follow-up visits and assessments are detailed in the Trial Assessment Schedule (see **Table 1** and **Figure 1****Error! Reference source not found.**).

Trial visit and contact schedules will be prepared for each child at randomisation, and children should be followed on that same schedule, until the final follow-up, even if their trial medication is discontinued prematurely (see **Section 0**). The target dates for trial contacts are determined by the date of randomisation and are not affected by subsequent events. The schedule defines visit dates (with windows) necessary for data collection.

Trial contacts are scheduled as follows:

- Trial entry (day 1): Baseline information will be collected, and a face-to-face assessment will be made
- Daily until discharge: face-to-face assessment will be made
- Day of discharge: face-to-face assessment and confirmation of contact details
- Week 1, 2, & 3: follow-up telephone call (or face-to-face if usual practice)
- Week 4: face-to-face follow-up (in exceptional circumstances, this visit may be conducted by telephone if the child is unable to attend the clinic/hospital)
- Acute events: face-to-face assessment if child returns to the randomising site

6.1.1 BASELINE INFORMATION

At randomisation, medical and relevant social history, including demographics and socioeconomics, documentation of any underlying diseases, mode of delivery, documentation of immunisation status (including taking copies of immunisation records where available), duration of symptoms to date and recent antibiotic exposure, will be recorded. Locator information, including physical address and contact phone numbers will also be collected. Anthropometry will include weight, height/length and mid-upper arm circumference (MUAC) (height/length and MUAC may be collected as soon as practicable post-baseline if not possible to assess at trial entry). Vital signs (respiratory and heart rate, oxygen saturation) and temperature will be measured. Relevant respiratory symptoms and signs will be solicited. Chest X-rays at randomisation will be strongly encouraged where site facilities allow, but are not mandatory. Where possible, and where available, digital copies of all chest X-ray images will be collected.

6.1.2 FACE-TO-FACE ASSESSMENT

A physical examination must be performed at each face-to-face assessment, including acute events if the child returns to the randomising site.

The following will be recorded for all face-to-face assessments:

- Vital signs (respiratory and heart rate, oxygen saturation) and temperature (during hospitalisation only)
- Symptoms and clinical signs, specific solicited side-effects and adverse events
- Concomitant care/healthcare utilisation
- Results of any haematology/biochemistry/microbiological investigations/chest X-rays undertaken as part of the usual standard of care, but not required by the trial

Children will be weighed on the day of step-down to oral antibiotics to ensure correct dosing and at the week 4 face to face visit.

If the child is in hospital at the week 4 visit (either still admitted from randomisation, or re-admitted), the total duration of that hospitalisation and resource use during it will be collected through to discharge (even though follow-up formally finishes 28 days after randomisation).

If the parent/carer did not bring the child's immunisation record at their original admission, they will be asked to bring it to the week 4 face to face visit, where it will be copied.

6.1.3 DAY OF DISCHARGE

At discharge, locator information collected at baseline will be verified together with two telephone numbers (wherever possible) which should both be called whilst the parents/carers are present to confirm that correct information has been provided. Tolerability of oral medication will be assessed in children who have stepped down to oral.

6.1.4 WEEKS 1, 2 & 3

Telephone contact will be made by sites to parents/carers of children who are not still in hospital at week 1, week 2 and week 3 (see [Table 1](#) for visit windows). Contact will be face-to-face if the child has not been discharged from hospital, or if this is part of normal standard of care at the site.

Sites may choose to re-schedule contacts to allow for public holidays or other unavoidable circumstances that affect the scheduled visit date, but the re-scheduled visit or contact should preferably be in the window period as detailed in the trial schema ([Table 1, Figure 2](#)).

6.1.4.A Telephone Contact

A review of clinical signs and symptoms must be performed at each telephone contact during follow-up. At a minimum, the following will be recorded:

- Standardised symptom checklist including review of cough, presence of rapid breathing, fever, general state and common known side effects of amoxicillin or co-amoxiclav.
- Solicited clinical adverse events since last protocol contact, including rashes, diarrhoea, vomiting, gastrointestinal events, and thrush/candida.
- Any acute illnesses requiring assessment by a healthcare provider (including traditional healers) since last protocol contact, including whether any antibiotic prescriptions were issued.
- Systemic antibiotic treatment since last protocol contact, including, as appropriate, adherence to PediCAP treatment and whether any additional/new antibiotic prescriptions were issued.
- Adherence and tolerability of PediCAP treatment, including any medication errors (week 1 only).
- Concomitant care/healthcare utilisation (including traditional healers).

6.1.5 ACUTE EVENTS

Parents/carers will be given a card with the contact details for the trial research team at their site, and encouraged to return to the site if the child becomes acutely unwell during the follow-up period. During any acute events, the child can be seen face-to-face if attending the randomising site. Otherwise, telephone contact can be arranged.

6.2 CHILDREN UNDERGOING PK SAMPLING

A total of 180 children will undergo PK sampling. This will consist of 60 children in the main trial (PediCAP-A) randomised to co-amoxiclav and receiving the standard co-amoxiclav 7:1 ratio (independently of total duration of antibiotic therapy randomisation). A further 120 children will be randomised to oral step-down with co-amoxiclav 4:1 versus 14:1 ratios (60 in each group) in a Phase II PK trial (PediCAP-B). The assessment schedule for these 120 additional children will be the same as for children in the main trial. For all patients undergoing PK sampling, additional informed consent will be sought for taking PK samples. Children will have up to 5 PK samples taken immediately before and then over up to 12h after their first morning dose. See [Section 10.1](#) for more details.

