^j If available (performed locally following standard of care; not to be done specifically for research), any relevant bacteriology results as well as any virology, for example rapid testing for RSV and Influenza A/B (any method) performed locally.

^k Results of any chest X-rays as reported at local site by radiology staff will be recorded; digital copies of the X-rays will be collected wherever possible.

Investigations to be carried out only in a subset of children at selected sites

^l Co-amoxiclav pharmacokinetics: up to 5 PK samples (2ml per sample) after the first oral dose taken in the morning (n=60 in the main trial (PediCAP-A), all 120 children in the Phase II PK trial (PediCAP-B))

^m Peri-rectal swab (or whole stool if passed or available from a nappy) at trial entry, discharge, and at d28 follow-up (n=330 in the main trial (PediCAP-A), 66 per site).

ⁿ A nasopharyngeal swab at trial entry, and at either discharge or d28 follow-up (i.e. two swabs per child) (same 330 children as peri-rectal swabs). The second swab being at discharge vs day 28 will be determined by randomisation to ensure comparability.

CONTENTS

GENERAL INFORMATION	3
LAY SUMMARY	9
TRIAL SCHEMA.....	11
SUMMARY OF TRIAL	12
TRIAL ASSESSMENT SCHEDULE.....	16
CONTENTS	18
ABBREVIATIONS	22
1 BACKGROUND	25
1.1 THE ADVERSE IMPACT OF SEVERE PNEUMONIA ON CHILD HEALTH IN AFRICA	25
1.2 THE ROLE OF OPTIMAL ANTIBIOTIC TREATMENT IN MANAGING SEVERE PNEUMONIA	25
1.2.1 Right Drug.....	25
1.2.2 Right Duration	26
1.2.3 Right Delivery	26
1.2.4 Right Dose	26
1.3 CURRENT WHO RECOMMENDATIONS	27
1.4 RATIONALE FOR DESIGN OF THE PEDICAP TRIAL	27
1.4.1 Rationale for Design of Oral-step Down Comparisons	28
1.4.2 Rationale for Design of Antibiotic Duration Comparisons	28
1.4.3 Rationale for Inclusion of “Benchmarking” Continuous Intravenous Group	30
1.4.4 Service Evaluation in Recruiting Sites	30
1.4.5 Dosing for PediCAP.....	31
1.5 GOALS OF PEDICAP	35
2 SELECTION OF SITES/CLINICIANS.....	37
2.1 SITE/INVESTIGATOR INCLUSION CRITERIA.....	37
2.1.1 PI's Qualifications & Agreements.....	37
2.1.2 Adequate Resources	38
2.1.3 Site Assessment.....	38
2.2 APPROVAL AND ACTIVATION.....	39
3 SELECTION OF CHILDREN	40
3.1 CHILD INCLUSION CRITERIA	40
3.2 CHILD EXCLUSION CRITERIA	41
3.3 NUMBER OF CHILDREN	42
3.3.1 Main Trial (PediCAP-A).....	42
3.3.2 PK Sampling.....	42
3.3.3 Microbiological Sampling	43
3.4 CO-ENROLMENT GUIDELINES.....	43
3.5 SCREENING PROCEDURES & PRE-RANDOMISATION INVESTIGATIONS	43

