3.1 CHILD INCLUSION CRITERIA

1. Aged 2 months to 6 years inclusive
2. Weighing ≥ 3 kg and <30 kg
3. Admitted to hospital with severe pneumonia judged to require at least 24h of intravenous antibiotics by the treating physician
4. Difficulty breathing (with or without cough reported by parent/carer) PLUS one or more of
 - a. Central cyanosis or hypoxaemia (room air pulse oximetry $<90\%$)
 - b. Any sign of severe respiratory distress (e.g. severe chest indrawing, grunting, nasal flaring, head nodding)
 - c. Signs of pneumonia (fast breathing (defined as respiratory rate ≥ 50 breaths per minute at age 2-11 months and ≥ 40 breaths per minute at age 1 years or older) or chest indrawing) PLUS a general danger sign (inability to breastfeed or drink, lethargy or reduced level of consciousness, convulsions, moderate/severe malnutrition)occurring at any time from admission up to randomisation.
5. About to initiate or already initiated intravenous benzylpenicillin plus gentamicin, ampicillin plus gentamicin, benzylpenicillin or ampicillin alone, ceftriaxone alone or cefotaxime alone
6. Received at most 24h of these intravenous antibiotics at the point of randomisation (that is, first dose of any intravenous antibiotics must have been administered no more than 24h previously at randomisation)
7. Parent/carer willing to accept and adhere to all possible randomised allocations for their child (including 5 days of intravenous antibiotics if joining PediCAP-A) and signed written informed consent available from parent/carer
8. Available for follow-up for the entire study period; specifically, parent/carer willing to return with their child to clinic at 4 weeks, and be contacted at minimum by telephone at weeks 1, 2 and 3

For children enrolled in PK ([Section 10.1](#)) or microbiology ([Section 10.2](#)) substudies, additional inclusion criteria are:

9. If undergoing additional PK sampling: willing to provide samples and potentially to stay in hospital for up to an additional 12h (separate consent will be obtained for PK sampling which may be refused and the child still join the main trial (PediCAP-A): consent for PK sampling is required for inclusion in the Phase II PK trial (PediCAP-B))

10. If undergoing additional microbiological sampling: willing to provide samples at enrolment, discharge and week 4 (separate consent will be obtained for microbiological sampling which may be refused and the child still join the main trial (PediCAP-A))

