The main criteria for moving from intravenous to oral antibiotics is that the child should have improved clinically, be currently clinically stable or continuing to improve, and be well enough to take medication by mouth, i.e. can ingest and keep down the dispersible tablets when made up in a small amount of liquid, and hence oral absorption of the antibiotic is likely to be good. Children may move to oral medication whilst inpatients (e.g. if they are still receiving supplemental oxygen). See MOP for further details.

Children should be discharged on oral medication as soon as they are clinically stable and have received and retained at least one dose of oral antibiotics. See MOP for further details.

Table 7: Dosing for oral amoxicillin and co-amoxiclav

FORMULATION	WEIGHT BAND	# TABLETS AM	# TABLETS PM	# TABLETS DAILY	DAILY DOSE (MG)
Amoxicillin (250mg tablets)	3 - <6kg	1	1	2	500
	6 - <10kg	2	1	3	750
	10 - <14kg	2	2	4	1000
	14 - <20kg	3	3	6	1500
	20 - <25kg	4	4	8	2100
	25 - <35kg	5	5	10	2500
Co-amoxiclav 7:1 (200/28.5mg tablets)	3 - <6kg	1	1	2	400/57
	6 - <10kg	2	2	4	800/114
	10 - <14kg	3	2	5	1000/142.5
	14 - <20kg	4	4	8	1600/228
	20 - <25kg	5	5	10	2000/285
	25 - <35kg	6	6	12	2400/342
Co-amoxiclav 4:1 (250/62.5mg)	3 - <6kg	1	1	2	500/125
	6 - <10kg	2	1	3	750/187.5
	10 - <14kg	2	2	4	1000/250
	14 - <20kg	3	3	6	1500/375
	20 - <25kg	4	4	8	2000/500
	25 - <35kg	5	5	10	2500/625
Co-amoxiclav 14:1 (150/10.725mg)	3 - <6kg	2	1	3	450/32.175
	6 - <10kg	3	2	5	750/53.625
	10 - <14kg	4	3	7	1050/75.075
	14 - <20kg	5	5	10	1500/107.25
	20 - <25kg	7	6	13	1950/139.425
	25 - <35kg	8	8	16	2400/171.6

Note: inclusion criteria include weights up to 30kg ([Section 3](#)), but dosing table includes weights up to 35kg to allow for dehydrated children gaining weight during admission, and to align with WHO HIV weight-bands.

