10.1.1 PHARMACOKINETIC SAMPLING IN CHILDREN RANDOMISED IN THE MAIN TRIAL (PEDI CAP-A)

A subset of children joining the main trial (PediCAP-A) will be approached for additional written informed consent to take part in a PK substudy of the 7:1 co-amoxiclav formulation if they are randomised to oral co-amoxiclav step-down. In total, 60 children with a complete set of PK samples (defined below) will be included (out of the total 500 randomised to 7:1 co-amoxiclav in PediCAP-A), targeting a minimum of 6 children per weight-band from 6kg up to 25kg to ensure a minimum dataset is generated for each proposed dose in the main weight range.

PK sampling will occur immediately before and then after the first morning dose and will consist of 5 samples per child weighing 6kg or more (2ml per sample); e.g. before observed dosing (5-10 min pre-dose), during early absorption (0.25-1h post dose), around the expected C_{max} (1-2h), during early disposition (2-6h), and in the terminal phase (6-12h). Optimal design and model-based stochastic simulation-estimation will be used to determine the exact sampling windows (which will maximise the information obtained from sampling compared to fixed sampling times) and the allocation of children between the weight-bands, while keeping the total pre-specified sample size. Allowable blood draws are 10ml or more in unwell children weighing 5kg or more ([Appendix II](#)): any child weighing less than 5kg will have one (4kg) or two (3kg) of the 5 PK samples dropped (chosen according to the optimal design) and will be considered to have a complete PK sample set (leading to total blood draws over 12h of 8ml and 6ml respectively). A cannula will be used to avoid repeated venepuncture, and anaesthetic cream to numb the child's skin.

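### The PK pre-dose sample is required whatever the dosing history, so it is expected to be blank in children whose first oral dose is that morning dose; criterion 9's 12 h of extra stay does not cover a child ready to go home the evening before

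*Protocol*

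**What the plan says.** **Sampling.** Section 6.2: "Children will have up to 5 PK samples taken immediately before and then over up to 12h after their first morning dose". Section 10.1.1 gives five 2 ml samples, introduced as examples. The first is "before observed dosing (5-10 min pre-dose" and the last is "in the terminal phase (6-12h" after the dose. Exact windows are left to optimal design and simulation. Section 10.1.2 applies the same scheme to PediCAP-B. Footnote l of Table 1 words it differently: "up to 5 PK samples (2ml per sample) after the first oral dose taken in the morning".

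**Earlier drug exposure.** Section 3.1, criterion 5, limits the IV regimens: "About to initiate or already initiated intravenous benzylpenicillin plus gentamicin, ampicillin plus gentamicin, benzylpenicillin or ampicillin alone, ceftriaxone alone or cefotaxime alone". Section 5.2.1 requires at least 24 h of IV treatment before any step-down to oral medication.

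**Stay.** Criterion 9 in section 3.1 asks that families be "willing to provide samples and potentially to stay in hospital for up to an additional 12h". The discharge text in section 5.3.1 reads: "Children should be discharged on oral medication as soon as they are clinically stable and have received and retained at least one dose". Section 9.2.2 excludes an additional PK day from length of stay. Section 10.1.1 speaks of an extra PK day with travel money, and its worked example is a child who would have left mid-morning and stays until the evening.

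**The concern.** The morning anchor creates two kinds of PK child. One took a first oral dose the evening before and may have a measurable trough. The other takes the first oral dose that morning and has had neither analyte as trial or permitted IV treatment. Sections 6.2 and 10.1.1 draw the pre-dose sample from both. In the second kind it says almost nothing about absorption or clearance, yet it is 2 ml of research blood from a sick young child. Table 1 does not mention a pre-dose sample, so a site reading the schedule and a site reading the section text could act differently.

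The anchor also affects the stay. A child given the first oral dose in the evening is not sampled until the next morning's dose and the hours after it. If that child could have gone home in the evening, the night counts as additional stay as well, and the 12 h in criterion 9 does not include it. Children without a complete sample set are replaced (section 10.1.1), so an early departure would mean sampling another child.

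**Working it through.** **1. Is the pre-dose sample blank?** None of the drugs in criterion 5 is amoxicillin or clavulanate, and the first oral dose follows at least 24 h of IV treatment. The one other source is community treatment: section 3.2 expects about 50% of children to have had a few oral or intramuscular doses, drug unspecified. The fraction left after t hours at half-life h is 2^(-t/h). With h = 1-3 h (assumed; not in the protocol) and t = 24 h:

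- h = 1: 2^(-24) = 0.000006%
- h = 3: 2^(-8) = 0.4%

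So zero or below quantification is the expected result. In a child who took an evening dose 12 h earlier, the fraction is 2^(-12) = 0.02% at h = 1 and 2^(-4) = 6% at h = 3. That trough can be informative, but how informative depends on the half-life.

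**2. Blood and sample counts.** The protocol's figures reproduce: 5 x 2 ml = 10 ml; 8 ml and 6 ml with one or two samples dropped; 60 + 120 = 180 PK children. Without the blank, a child gives 4 informative samples and 4 x 2 = 8 ml.

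**3. Value of a fifth post-dose sample.** All parameters here are assumed: a one-compartment oral model; half-life 1-1.5 h; absorption rate constant (ka) 1.2-3 per hour; 20% residual error; between-child variability of 40% in clearance (CL) and volume (V) and 70% in ka. Post-dose samples are at 0.6, 1.5, 4 and 9 h, with one more at 1, 2.5 or 6 h. J is the matrix of derivatives of log concentration with respect to log CL, log V and log ka; Ω = diag(0.16, 0.16, 0.49); σ² = 0.04.

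- Individual: variance matrix = (JᵀJ/σ² + Ω⁻¹)⁻¹. The log-CL variance ratio, five samples against four, is 0.75-0.96, a fall of 4-25%. The smallest gains come from the 6 h sample.
- Population, 60 children: variance matrix = [60 Jᵀ(JΩJᵀ + σ²I)⁻¹J]⁻¹. Log-CL variance falls by 0.3-2.4%, and the standard error goes from about 0.054 to 0.053. The fall is at most about 9% for volume and 11% for ka.

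The population gain in clearance is small because between-child variability sets a floor: √(0.4²/60) = √(0.16/60) = 0.052. The calculation treats every child as a morning starter, so it is an upper bound for a mixed group.

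**4. Extra stay.** Let g be the gap from the evening to the morning dose, L the time of the last sample after the morning dose (6-12 h), and d the time after the evening dose at which the child would otherwise leave. Extra stay = g + L - d.

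| Otherwise discharged | g | Extra stay |
|---|---|---|
| At the morning dose (d = g) | any | 6-12 h |
| Mid-morning (assumed d = g + 2) | any | 4-10 h |
| Same evening (assumed d = 1) | 12 h | 12 + 6 - 1 = 17 to 12 + 12 - 1 = 23 h |
| Same evening (assumed d = 1) | 10-14 h | 15-25 h |

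The first row reproduces criterion 9's 12 h, and the second matches the example in section 10.1.1. Only the same-evening rows exceed it. The 12 h gap is nominal twice-daily dosing; the protocol gives no clock times.

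**The case against.** A pre-dose blank is a normal baseline and can reveal undocumented earlier dosing, which matters when about half the children had community antibiotics. The five times are examples, windows are left to optimal design, section 6.2 says up to five samples, and section 10.1.3 refers procedures to a PK manual that is not shown. Each child's draw stays within the stated blood limits. All of this stands, and it is why the point is minor. It does not remove it, because 6.2 and 10.1.1 still fix one draw before the dose without condition, and Table 1 does not match.

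On the stay, the protocol partly foresees more than 12 h: it costs and pays for an extra PK day and says the stay will be clearly explained. The consent pages are not in this copy, so nothing can be said about what families are told there. Criterion 9 still carries the shorter figure.

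A reader might infer that evening starters are kept 24-26 h when families agreed to 12 h. That does not follow. Those figures run from the evening dose to the last sample, whereas criterion 9 concerns stay beyond the discharge that would otherwise occur. Reaching 24 h needs a last sample at the full 12 h, and 26 h also needs a 14 h dosing gap that the protocol does not state. A child who would have stayed overnight anyway is within 12 h.

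**Conclusion.** The point holds as a minor design and wording matter. In morning starters one of five samples is expected to be blank. This rests on the permitted IV list and the 24 h minimum, with negligible carry-over from community doses under assumed half-lives of 1-3 h. To call it a certain zero would go slightly too far, because those community drugs are not specified.

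The analytic cost is small. A reader might take the individual log-clearance gain (4-25%) as the loss to the PK study. The planned analysis is a pooled population model, where log-clearance variance changes by 0.3-2.4% under the assumed parameters. The protocol does not say what share of children start in the morning, so no total of blank samples or blood volume can be claimed.

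Criterion 9 is too short only for a child who would otherwise leave before the morning dose: about 17-23 h extra with a 12 h gap and discharge about 1 h after the evening dose. Section 5.3.1 allows that case; how often it occurs is unknown. PK stay is excluded from length of stay, so no main-trial endpoint is affected.

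**What to change.** 1. Reconcile footnote l of Table 1 with sections 6.2 and 10.1.1 on whether a sample precedes the dose.
2. In 6.2 and 10.1.1, take the pre-dose sample only if an oral trial dose has already been given. Otherwise let the planned optimal design place it after the dose, or omit it (8 ml instead of 10 ml), and count the set as complete. The rule for children under 5 kg in 10.1.1 already counts a reduced set as complete.
3. Restate the extra stay in criterion 9 to cover a child whose first oral dose is in the evening and who could otherwise leave that evening (up to about 24 h: 12 h gap plus 12 h sampling). Align it with the additional day in 9.2.2 and the extra PK day in 10.1.1, and check that the PK consent text agrees.

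The cost is wording in the protocol and PK manual, and in the consent text if it repeats the 12 h. The downside is two sampling schedules instead of one, and no blank in morning starters to check for undocumented earlier dosing.
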